8.3.4.3. Systemic Events

During the reactogenicity e-diary reporting period, participants will be asked to assess vomiting, nausea, diarrhea, headache, fatigue, chills, new or worsened muscle pain, and new or worsened joint pain and to record the symptoms in the reactogenicity e-diary. The symptoms will be assessed by the participant as absent, mild, moderate, or severe according to the grading scale in Table 2.

If a systemic event persists beyond the end of the reactogenicity e-diary period following vaccination, the investigator will enter this information into the CRF and follow up at the next study visit to obtain stop dates for the events that have resolved.

If a Grade 3 systemic event is reported in the reactogenicity e-diary, a telephone contact should occur to ascertain further details and determine whether a site visit is clinically indicated. Only an investigator or medically qualified person can classify a participant's systemic event as Grade 4. If a participant experiences a confirmed Grade 4 systemic event, the investigator must immediately notify the sponsor and, if it is determined to be related to the administration of the study intervention, further vaccinations will be discontinued in that participant.

Table 2. Systemic Event Grading Scale

	Mild Grade 1	Moderate Grade 2	Severe Grade 3	Grade 4ª
Fatigue (= tiredness)	Does not interfere with activity	Some interference with activity	Prevents daily routine activity	Emergency room visit or hospitalization for severe fatigue
Headache	Does not interfere with activity	Some interference with activity	Prevents daily routine activity	Emergency room visit or hospitalization for severe headache

a. Only an investigator or qualified designee can classify a participant's local reaction as Grade 4, after clinical evaluation of the participant or documentation from another medically qualified source (eg, emergency room or hospital record) or contact with the participant. Grade 4 local reactions will be collected on the AE CRF and assessed by the investigator using the AE intensity grading scale as detailed in Section 10.3.3.

Table 2. Systemic Event Grading Scale
Mild Modera

	Mild Grade 1	Moderate Grade 2	Severe Grade 3	Grade 4ª
Vomiting	1 to 2 times in 24 hours	>2 times in 24 hours	Requires intravenous hydration	Emergency room visit or hospitalization for severe vomiting

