10.9.5. Objectives, Endpoints, and Estimands (Substudy A)

Objectives	Endpoints	Estimands	
Primary Safety	Primary Safety	Primary Safety	
To evaluate the safety profile of combination RSVpreF + qIRV	 Local reactions (pain at the injection site, redness, and swelling) Systemic events (fever, fatigue, headache, vomiting, nausea, diarrhea, chills, new or worsened muscle pain, and new or worsened joint pain) AEs SAEs 	In participants receiving at least 1 dose of study intervention, the percentage of participants reporting: • Local reactions within 7 days following each vaccination • Systemic events within 7 days following each vaccination • AEs within 1 month after each vaccination • SAEs throughout the study	
Primary Immunogenicity	Primary Immunogenicity	Primary Immunogenicity	
To describe the immune responses elicited by combination RSVpreF + qIRV in comparison with those elicited by RSVpreF alone	RSV A and RSV B NTs	In participants in compliance with the key protocol criteria (evaluable participants): • GMR of NTs for each RSV subgroup (A or B) 1 month after vaccination with combination RSVpreF + qIRV to that with RSVpreF alone (sequential-administration group, Visit A103)	
To describe the immune responses elicited by combination RSVpreF + qIRV in comparison with those elicited by qIRV alone	Strain-specific HAI titers for the current seasonal strains (2×A, 2×B) recommended by WHO for recombinant or cell-based influenza vaccines	In participants in compliance with the key protocol criteria (evaluable participants): GMR of strain-specific HAI titers 1 month after vaccination with combination RSVpreF + qIRV to that with qIRV alone (sequential-administration group, Visit A102)	

Objectives	Endpoints	Estimands
Exploratory	Exploratory	Exploratory

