2.2.1.3. Primary Safety Estimands

The primary estimands for the safety objective will use the treatment policy strategy and estimate the safety rate regardless of whether an intercurrent event occurs.

DMB02-GSOP-RF02 7.0 Statistical Analysis Plan Template 31-Jan-2022 PFIZER CONFIDENTIAL TMF Doc ID: 98.03 Page 10 of 46

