Systemic events within 7 days after vaccination	Systemic events reported within 7 days after Vaccination 1 among participants who received the combination vaccine at Visit A101 with at least 1 day of e-diary data transferred following the vaccination.	Systemic events reported within 7 days after Vaccination 1 or after Vaccination 2 among participants who received qIRV at Visit A101 with at least 1 day of e-diary data transferred following vaccination and received RSVpreF at Visit A102 with at least 1 day of e-diary data transferred following vaccination.	Systemic events reported within 7 days after Vaccination 1 among participants who received qIRV at Visit A101 with at least 1 day of e-diary data transferred following the vaccination.	Systemic events reported within 7 days after Vaccination 2 among participants who received RSVpreF at Visit A102 with at least 1 day of e-diary data transferred following the vaccination.	Systemic events reported within 7 days after Vaccination 2 among participants who received placebo only at Visit A102 with at least 1 day of e-diary data transferred following the vaccination.
AEs within 1 month after vaccination	AEs reported from Vaccination 1 to before Vaccination 2 among participants who received the combination at Visit A101.	AEs reported from Vaccination 1 throughout the study among participants who received qIRV at Visit A101 and RSVpreF at Visit A102.	AEs reported from Vaccination 1 to before Vaccination 2 among participants who received qIRV at Visit A101.	AEs reported from Vaccination 2 through the end of the study among participants who received RSVpreF at Visit A102.	AEs reported from Vaccination 2 through the end of the study among participants who received placebo only at Visit A102.
SAEs throughout the study	SAEs reported from Vaccination 1 throughout the study among participants who received the combination at Visit A101.	SAEs reported from Vaccination 1 throughout the study among participants who received qIRV at Visit A101.	N/A	N/A	N/A

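### In three of its four rows, the sequential qIRV/RSVpreF safety column counts only participants who received both injections, which conflicts with the at-least-one-dose, treatment-policy safety estimand

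*SAP*

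**What the plan says.** The table in SAP 3.1.3 (Primary Safety Endpoints) lists five as-received vaccine groups for Substudy A. The populations that matter here are:

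- Sequential column, AE row: AEs from Vaccination 1 to study end "among participants who received qIRV at Visit A101 and RSVpreF at Visit A102".
- Sequential column, local-reaction and systemic-event rows: both injections, with at least one e-diary day after each. The second half of the systemic-event condition reads "received RSVpreF at Visit A102 with at least 1 day of e-diary data transferred following vaccination".
- Sequential column, SAE row: "SAEs reported from Vaccination 1 throughout the study among participants who received qIRV at Visit A101". The second injection is not required.
- qIRV-alone column, AE row: "AEs reported from Vaccination 1 to before Vaccination 2 among participants who received qIRV at Visit A101".
- Combination column, AE row: "AEs reported from Vaccination 1 to before Vaccination 2 among participants who received the combination at Visit A101".

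Protocol 10.9.5 opens the Substudy A safety estimand with "In participants receiving at least 1 dose of study intervention, the percentage of participants reporting", and SAP Table 2 repeats it. SAP 2.2.1.3 adopts a treatment-policy strategy, which will "estimate the safety rate regardless of whether an intercurrent event occurs". SAP 2.2.1.3.1 and 2.2.1.3.2 keep all data collected after an intercurrent event, and SAP 2.2.1.1 lists failure to receive the intervention as randomized among those events. SAP 2.1 declares no change from the protocol's analysis.

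**The concern.** Whether a participant receives RSVpreF at Visit A102 is known only after qIRV has been given and its reactions observed. For a confirmed Grade 4 systemic event judged related to study intervention, Protocol 8.3.4.3 states that "further vaccinations will be discontinued in that participant". Protocol 8.3.4.2 has the same rule for local reactions, and Protocol 7.1 lists AEs among the reasons for discontinuing study intervention. A both-injection filter can therefore remove a participant because of the outcome being measured, from numerator and denominator alike.

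The data are not missing by design. Protocol 7.1 asks that participants who discontinue vaccination stay in the study for safety evaluation, and Protocol 10.9.10.6.4 schedules safety follow-up for early withdrawals.

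At stake is the reading of one of the SAP's primary safety groups. A rate labelled as that of the sequential regimen would describe those who completed it, and the reader would not be told.

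**Working it through.** **1. Text comparison (no assumptions needed).**

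| Source | Requires RSVpreF at A102? | Diary requirement |
|---|---|---|
| Safety estimand, Protocol 10.9.5 and SAP Table 2 | No, at least one dose | None |
| Safety population, SAP Section 4 | No | None |
| E-diary safety population, SAP Section 4 | No | At least one day |
| Sequential column: local reactions, systemic events | Yes | At least one day after each injection |
| Sequential column: AEs | Yes | None |
| Sequential column: SAEs | No | None |
| qIRV-alone and combination columns: AEs | No | None |

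Three consequences follow.

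- The sequential column uses two populations: two-dose recipients in three rows and all qIRV recipients in the SAE row.
- SAP 3.1.3.3 derives AEs leading to study withdrawal for all five groups, and for the sequential group after both vaccinations. A participant withdrawn before Visit A102 because of an AE after qIRV cannot enter that column's AE row.
- A participant with both injections and a diary only after the first belongs to the e-diary safety population but is dropped from the sequential reactogenicity rows.

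**2. Size.** The documents give no dose-2 dropout rate and no event rate. The 10% in Protocol 10.9.11.5 is a nonevaluable rate for the immunogenicity populations (125 × 0.90 = 112.5, stated as about 110) and does not supply one. The only documented input is N = 125 per group; everything else below is assumed.

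Let r be the rate in two-dose recipients, d the number who miss dose 2, and p the rate among those d.

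Rate in all starters = [r(125 − d) + p·d] / 125, so the difference from r is (d/125)(p − r).

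With r = 0.30:

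| d | p | Calculation | All starters |
|---|---|---|---|
| 6 | 0.60 | (35.7 + 3.6)/125 | 31.4% |
| 6 | 1.00 | (35.7 + 6.0)/125 | 33.4% |
| 12 | 0.60 | (33.9 + 7.2)/125 | 32.9% |
| 12 | 1.00 | (33.9 + 12.0)/125 | 36.7% |
| 12 | 0.15 | (33.9 + 1.8)/125 | 28.6% |

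The sign changes at p = r. The column is too low by 1.4 to 6.7 percentage points in the first four rows and too high by 1.4 points in the last.

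**3. Rare against common events.** Suppose x of 125 qIRV recipients had the event, k of those x missed dose 2, and nobody else did. The both-dose rate is (x − k)/(125 − k). Intervals are Clopper-Pearson 95%.

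| x | k | All qIRV recipients | Both-dose subset |
|---|---|---|---|
| 5 | 3 | 4.0% (1.3–9.1) | 2/122 = 1.6% (0.2–5.8) |
| 5 | 5 | 4.0% (1.3–9.1) | 0/120 = 0.0% (0.0–3.0) |
| 10 | 3 | 8.0% (3.9–14.2) | 7/122 = 5.7% (2.3–11.5) |
| 25 | 5 | 20.0% (13.4–28.1) | 20/120 = 16.7% (10.5–24.6) |
| 80 | 5 | 64.0% (54.9–72.4) | 75/120 = 62.5% (53.2–71.2) |

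Here all who miss dose 2 had the event, so the difference can go only one way. The scenarios show relative exposure: a rare severe event can vanish from the column, while a common reaction barely moves.

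**The case against.** The strongest reply is that the protocol's estimand is per vaccination and is already met. Reactions and AEs are wanted after each vaccination; the qIRV-alone column takes every qIRV recipient and the RSVpreF-alone column covers the second injection. The sequential column is extra pooling across doses. SAP 2.2.1.3.1 and 2.2.1.3.2 define its treatment as qIRV followed by RSVpreF, and the table is as received, so someone given qIRV only arguably did not receive that treatment. No hypothesis is tested, and no between-group difference is planned for reactogenicity or general AEs.

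Much of this stands. The per-vaccination rates are sound, and part of the conflict lies within the SAP's own estimand text: a two-injection treatment condition against at least one dose under treatment policy. It does not explain why the SAE row of the same column ignores dose 2, or why AEs leading to withdrawal are derived for a group from which withdrawals before A102 are barred. The SAP also lists this column among its primary safety groups and does not label it a completer subset.

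The reply also rules out some stronger readings:

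- A reader might infer that reactions which stopped vaccination are lost from the report. They are not. They stay in the qIRV-alone column, subject to one diary day for reactogenicity. Those meeting a seriousness criterion also enter the sequential SAE row, and SAP 6.4.2 tabulates withdrawals before each visit with reasons.
- A reader might infer that the filter is what makes the sequential and combination AE columns non-comparable. They already differ: one injection up to Vaccination 2 against two injections through study end. The like-for-like AE contrast is combination against qIRV alone, and it is unaffected.

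**Conclusion.** The inconsistency is established from the text alone for the local-reaction, systemic-event and AE rows of the sequential column. Those rows condition on a post-baseline event related to tolerability of qIRV, contrary to the at-least-one-dose population and the treatment-policy strategy, and they disagree with the SAE row. It would be wrong to say that the whole safety column is restricted to two-dose recipients.

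It is also tempting to conclude that the sequential rates are understated. The documents do not support a direction. Participants can miss dose 2 for reasons unrelated to reactions, such as their own request, a protocol deviation or loss to follow-up (Protocol 7.1 and 7.2). They have had one injection and may have been observed for less time, so their event rate could lie below that of two-dose recipients. The worked range of 28.6% to 36.7% around an assumed 30% rests wholly on assumed dropout and event rates. If few participants miss dose 2, the effect on common reactions will be small. Rare severe events and AEs leading to withdrawal are the most exposed. The point deserves correction because it affects a primary safety group and costs little to put right.

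**What to change.** In the SAP 3.1.3 table, base the local-reaction, systemic-event and AE rows of the sequential column on all participants who received qIRV at Visit A101, as received, matching the SAE row. Count events after whichever vaccinations were given. For the two reactogenicity rows, require e-diary data after at least one vaccination, in line with the e-diary safety population. Align the fifth treatment condition in SAP 2.2.1.3.1 and 2.2.1.3.2 with this population, and footnote the number who contributed one vaccination only. If a both-dose summary is still wanted, label it a completer subset outside the primary estimand.

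The cost is wording in one table and two estimand sections, and a change of denominator; no new data are needed. The downside is that some participants will contribute one injection and less follow-up to a column named for two, which the footnote makes visible.

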3.1.3.1. Local Reactions Within 7 Days After Vaccination

The local reactions include redness, swelling, and pain at the injection site from Day 1 through Day 7 after vaccination, where Day 1 is the day of vaccination with combination RSVpreF + qIRV, qIRV, RSVpreF, or placebo.

This section describes derivations with details for the assessment of local reactions: any presence, maximum severity, duration, and onset day of local reactions, in addition to the presence of local reactions on each day, for each of the 5 vaccine groups as mentioned above.

DMB02-GSOP-RF02 7.0 Statistical Analysis Plan Template 31-Jan-2022 PFIZER CONFIDENTIAL TMF Doc ID: 98.03 Page 19 of 46

3.1.3.1.1. Presence of Local Reactions Within 7 Days After Vaccination

For the summary of the presence (yes or no) of a local reaction during the interval from Day 1 through Day 7 after vaccination, where Day 1 is the day of Vaccination 1 or Vaccination 2, the following 2 variables are derived for each participant included in the reactogenicity subset:

1. Presence (yes or no) of each local reaction on any day (Day 1 through Day 7).

The derivation is described in Table 3.

 Table 3.
 Derived Variables for Each Local Reaction

Variable ^a	Yes (1)	No (0)	Missing (.)
Any day	The participant reports the	The participant reports the	The participant reports the
(Days 1-7)	reaction as "yes" on any day	reaction as "no" on all 7 days	reaction as missing on all
	(Days 1-7).	or as a combination of "no"	7 days.
		and missing on all 7 days.	

a. The variable will be defined for each of the 3 local reactions.

2. Presence (yes or no) of any local reaction on any day (Day 1 through Day 7).

For any local reaction on any day, a similar definition can be applied as given in Table 4.

 Table 4.
 Derived Variables for Any Local Reaction

Variable	Yes (1)	No (0)	Missing (.)
Any day	The participant reports any	The participant reports all	The participant reports all
(Days 1-7)	local reaction as "yes" on any	reactions as "no" on all 7 days	local reactions as missing
	day (Days 1-7).	or as a combination of "no"	on all 7 days.
		and missing on all 7 days for	
		all 3 local reactions.	

3.1.3.1.2. Maximum Severity of Local Reactions Within 7 Days After Vaccination

The grading of local reactions is listed in Table 5.

 Table 5.
 Grading Scale for Local Reactions

	Mild Grade 1	Moderate Grade 2	Severe Grade 3 ^a	Grade 4 ^b
Redness	2.5 cm to 5.0 cm	>5.0 cm to 10.0 cm	>10 cm	Necrosis or exfoliative
	(5 to 10 measuring	(11 to 20 measuring	(>20 measuring	dermatitis
	device units from	device units from the	device units from	
	the e-diary) or mild	e-diary) or moderate	the e-diary) or	
	from the AE CRF.	from the AE CRF.	severe from the AE	
			CRF.	

DMB02-GSOP-RF02 7.0 Statistical Analysis Plan Template 31-Jan-2022 PFIZER CONFIDENTIAL TMF Doc ID: 98.03 Page 20 of 46

	Mild	Moderate	Severe	Grade 4 ^b
	Grade 1	Grade 2	Grade 3 ^a	
Swelling	2.5 cm to 5.0 cm	>5.0 cm to 10.0 cm	>10 cm	Necrosis
_	(5 to 10 measuring	(11 to 20 measuring	(>20 measuring	
	device units from	device units from the	device units from	
	the e-diary) or mild	e-diary) or moderate	the e-diary) or	
	from the AE CRF.	from the AE CRF.	severe from the AE	
			CRF.	
Pain (at the	Does not interfere	Interferes with	Prevents daily	Emergency room visit or
injection site)	with activity (mild	activity (moderate	activity (severe	hospitalization for severe
	from the e-diary or	from the e-diary or	from the e-diary or	pain at the injection site.
	the AE CRF).	the AE CRF).	the AE CRF).	

 Table 5.
 Grading Scale for Local Reactions

a. The maximum reaction size in measuring device units is 21 (10.5 cm). Any reaction size >21 measuring device units is recorded as a number that is >20 (eg, 21) in the e-diary.

b. Grade 4 assessment should be made by the investigator using the AE severity grading scale. The assessment will be collected on the AE CRF and thus not reported from the e-diary.

The following variables are derived for each participant included in the reactogenicity subset:

1. Maximum severity of each local reaction on any day (Day 1 through Day 7).

The maximum severity (highest grading) of each local reaction within 7 days after vaccination will be derived. The maximum severity will be derived as follows:

= Missing, if values are missing for all days (Day 1 through Day 7).

= 0, if the participant reports all reactions as "no" or a combination of missing and "no" for all days (Day 1 through Day 7).

= *Highest grade* (maximum severity) within 7 days after vaccination, if the answer is not "no" for at least 1 day.

2. Maximum severity of any local reaction on any day (Day 1 through Day 7).

The maximum severity for any local reaction will be derived as follows:

= Missing, if values are missing for all days (Day 1 through Day 7) across all 3 local reactions.

= 0, if the participant reports all reactions as "no" or a combination of missing and "no" for all days (Day 1 through Day 7) for all individual local reactions.

= *Highest grade* (maximum severity) within 7 days after vaccination, if the answer is not "no" for at least 1 day for at least 1 local reaction.

For the vaccine group receiving sequential administration of qIRV/RSVpreF, the maximum severity will be derived as the highest severity grade across Vaccination 1 and Vaccination 2. DMB02-GSOP-RF02 7.0 *Statistical Analysis Plan Template* 31-Jan-2022

PFIZER CONFIDENTIAL TMF Doc ID: 98.03 Page 21 of 46

